The force will be defined relative to maximum voluntary contraction for each hand separately. This allows even low-functioning participants to perform the task with the paretic hand. The participants will receive the instruction to follow the imperative cue by adjusting their own grip force. Feedback will be provided about the actual grip force in real-time. Force adjustment happens in stepwise increments of the relative force, which allows to induce two different implicit learning modes. Specifically, the volunteers will learn the association between visual cue and individual force level (1st order) within standard serial reaction time task⁴⁹, in which a sequence of force levels is provided repetitively and contrasted with random force levels. In addition, they will learn the hidden rule, i.e., the 2nd order sequence that can occur among both, the first-order sequential and the random force levels. This hidden regularity will be implemented through the sequential variation of cue intervals comparable to a morse code that occurs among otherwise uniform intervals. Based on the recorded muscle force (1000Hz sampling rate), the behavioral outcome (temporal/spatial accuracy) is monitored continuously throughout the learning phase. This procedure makes it possible to differentiate performance in the two learning modes. Furthermore, as left and right hand will be tested, it will be possible to estimate the impact of hand-dominance and side of lesion (non-/paretic hand) on the learning capacity for each learning mode.

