For the learning task-based data, a general linear model (GLM) will be fitted to each individual's data serving as the basis for the representational similarity analysis (RSA). In addition to the regressors of interest (matched to the onset time of each regressor of the event-related design of the learning-paradigm: 1st and 2nd order sequence force cues, random force cues) six motion parameters will be included as nuisance covariates. Estimated beta-values will be extracted from the GLM for each stimulus and run for each region of interest (ROI) within subject. For each ROI, a neural matrix will be created by correlating (Pearson) the multi-voxel patterns between all possible combinations of pairs of stimuli of the learning task condition and then averaged across subjects within group (first-order RSA⁵¹). In the second step, group-averaged matrices (only the upper diagonal elements) will be vectorized and correlated (Pearson) for all possible combinations of ROI pairs (second-order RSA⁵¹), which will allow to investigate the representational similarity between ROIs i.e., the clustering/networks of ROIs, with regard to the between-condition similarity in multi-voxel activation patterns.

For the resting-state data, the connectivity analysis will be used to identify physiological biomarkers for recovery and potential predictors for learning efficiency. For this purpose whole-brain resting-state network fluctuations, based on BOLD signal time courses, will be extracted for cortical and subcortical ROIs. Nuisance regression will be performed to account for the effects of motion on functional connectivity (including six translation and rotation parameters from the motion correction transformation, average CSF, white matter, and whole-brain time courses, as well as the first derivatives, squares, and squared derivatives of each of these confound predictors⁵². To extract the dynamic modulation of connectivity over time, time courses will be divided into sub-blocks of multiples of the TR to allow capturing slow-frequency fluctuations by approximating the frequency envelope of the hemodynamic response at the given TR with the highest possible temporal precision. Connectivity will be quantified as the magnitude-squared coherence^{53,54} between each pair of ROI for each sub-block of time⁵⁵. Network characteristics and their temporal dynamics will then be analyzed with dynamic network statistics following the approach given in reference⁵⁵.

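### No task-performance or learning measure enters the Aim 1 task-fMRI analysis, so stroke-control differences in performance could be mistaken for altered learning networks

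*Combined protocol and SAP*

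**What the plan says.** Aim 1 sets out to characterise motor-learning-related network dynamics from task fMRI in 25 stroke survivors and 15 controls.

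- **Behaviour (D1.4, Two-layered Learning Task).** Grip force is sampled at 1000 Hz and "the behavioral outcome (temporal/spatial accuracy) is monitored continuously throughout the learning phase". The section adds: "This procedure makes it possible to differentiate performance in the two learning modes". Force targets are scaled to each hand's maximum voluntary contraction (MVC), and sequence cues are contrasted with random cues.
- **First-level model (D3.2).** The regressors of interest are "1st and 2nd order sequence force cues, random force cues", and "six motion parameters will be included as nuisance covariates".
- **RSA (D3.2).** Each ROI's matrix is computed within participant and "then averaged across subjects within group". In the second step, "group-averaged matrices (only the upper diagonal elements) will be vectorized and correlated (Pearson) for all possible combinations of ROI pairs".
- **Covariates (D3.3).** Sex, age, race and ethnicity are named, for follow-up analyses.
- **Resting state (D3.2).** Connectivity is to identify "potential predictors for learning efficiency". Learning efficiency is not defined.

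**The concern.** A result described as learning-related needs two things: evidence that learning took place, and some means of separating a difference in the network from a difference in how well the task was done. The plan records the data for both and analyses neither in the Aim 1 comparison.

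A performance gap is plausible here. D1.2 admits stroke participants from MRC grade 2 grip force upward, and D1.4 expects low-functioning participants to work with the paretic hand. Larger errors, later responses or less learning could each change multi-voxel patterns.

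Two uses of the results are at stake. D3.1 makes effect sizes for the follow-up proposal a primary goal, and section B says that altered dynamics in the stroke group will supply targets for brain stimulation. A performance artefact would pass into both.

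**Working it through.** The plan gives no figure on this point, so there is none to reproduce. The check follows the behavioural record through the analysis and then asks what happens if performance differs between groups.

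**Step 1. Where could performance enter the Aim 1 task analysis?**

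| Stage | What the plan puts in | Performance or learning? |
|---|---|---|
| First-level GLM (D3.2) | Cue regressors, six motion parameters | No |
| First-order RSA (D3.2) | Correlations between stimulus patterns, averaged within group | No |
| Second-order RSA (D3.2) | Correlations between ROIs of group-averaged matrices | No; no participant-level data remain |
| Covariates (D3.3) | Sex, age, race, ethnicity | No |
| Univariate connectivity (D3.4) | Mentioned, no model given | None named |
| Behavioural test of learning (D3) | None | No |

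**Step 2. Does averaging within group remove a performance effect?** Write one matrix element for participant i as M_i = m + b × P_i + e_i, where P_i is performance and m is the same in both groups (no network difference at equal performance). Averaging within group gives m + b × mean(P) + mean(e). The expected stroke-control difference in that element is therefore

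b × (mean P in stroke − mean P in control).

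Averaging removes noise but leaves this term. If b were identical for every stimulus pair, the term would be a constant shift, which a Pearson correlation between ROIs ignores. If b varies across pairs, as it may when sequence and random cues respond differently to error or timing, the second-order correlations can change.

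**Step 3. How large could it be?** Take a participant-level network summary, linear in performance with the same slope in both groups and no true difference at equal performance. In within-group SD units,

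apparent group difference = ρ × D,

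where ρ is the within-group correlation of performance with the summary and D is the group gap in performance. The documents give neither, so the values below are assumptions:

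- ρ = 0.3, D = 0.5: 0.3 × 0.5 = 0.15 SD
- ρ = 0.4, D = 1.0: 0.4 × 1.0 = 0.40 SD
- ρ = 0.5, D = 1.5: 0.5 × 1.5 = 0.75 SD
- ρ = 0 or D = 0: 0 SD

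This shows that the route can matter, not that it will. The plan does not at present compute a participant-level summary, so the figures illustrate the mechanism and do not predict the planned output.

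**Step 4. Do the design features close the route?** MVC scaling equalises the relative force target, not the error or timing achieved against it. The random condition gives a within-person comparison, but the sequence-random difference itself depends on how much was learned. Neither makes D zero.

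**The case against.** The strongest case against the point has four parts.

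**Behaviour is linked to neural data elsewhere.** A reader might infer that no behavioural measure enters any neural analysis. The documents do not support that. D3.2 relates resting-state connectivity to learning efficiency, Aim 2 integrates upper-extremity function with network dynamics in the stroke group, and the imaging section of D1.4 foresees secondary analyses involving brain and behavioural outcomes. These stand as counter-examples to the broad reading. None is specified in detail, and none adjusts the stroke-control task comparison.

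**The design anticipates unequal ability.** Besides MVC scaling and random cues, there is real-time force feedback, mock-scanner familiarisation and a pilot phase to test feasibility across levels of motor function. D1.4 also says performance in the two learning modes can be distinguished. These features make a gap smaller or less likely, so the right word is could, not would. They do not replace an analysis, and D3 supplies none.

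**No formal group test is planned.** A reader might want to turn the bias into a false-positive rate, or set it beside the effect-size range in D3.1. Neither is warranted: D3.2 specifies no participant-level between-group test, and the D3.1 range describes within-group pre/post effects.

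**Adjustment may remove the signal.** Performance may be a consequence of the lesion's effect on the network. Conditioning on it can then take out part of a real effect, and trial-wise error or response-time regressors can absorb the sequence-random distinction itself. This stands, and it limits what the fix may demand.

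Section C describes a proof-of-concept pilot, and D3.4 concedes limited power for generalisability. That lowers the stakes, but the effect sizes are meant to be carried forward.

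**Conclusion.** The concern holds for the Aim 1 task-fMRI GLM and RSA. Followed as written, the plan does not use the recorded accuracy in the stroke-control comparison and does not test whether either group learned. It therefore cannot distinguish an altered learning network from worse performance or less learning.

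The size is unknown. It depends on the performance gap and its relation to the network measures, and the illustrative 0.15 to 0.75 SD rests wholly on assumed inputs. With no gap there is no bias by this route. The documents do not show that the confusion will occur, only that the plan could not detect it. The change should be made, because the results feed a later study and the data are already being collected.

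**What to change.** 1. **Define and report learning.** Compute a score per participant, hand and layer (random minus sequence error or response time, by run), naming the reference cues for each layer in advance. Report it in each group with its interval. Use the same score to define learning efficiency in the resting-state analysis.
2. **Move the RSA to participant level.** Compute the second-order summary for each participant before any group averaging. Report the stroke-control contrast both without and with the performance and learning scores as covariates. State that the first describes the overall group difference and the second the difference at equal performance and learning, and that they answer different questions because performance may mediate the lesion effect.
3. **Sensitivity analysis only.** Refit the first-level GLM with trial-wise force-error and response-time modulators.
4. **Wording of results.** Describe a group difference as learning-related only where the behavioural data show learning. Do not require that it survive adjustment.

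**Cost.** No new data are needed. There is some extra analysis, including a change to the RSA pipeline. Participant-level matrices will be noisier than group averages, and the adjusted estimate may remove part of a real effect, which is why both estimates are reported.

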Sleep and vigilance screening. General sleep quality is quantified with the Pittsburgh Sleep Quality Index (PSQI)⁴³ once in session 2. Sleep duration and quality of the night preceding each individual experimental session are assessed with the respective items of the St. Mary's sleep questionnaire⁴⁴. Before the task training and retest sessions, self-perceived vigilance is evaluated with the Stanford Sleepiness Scale (SSS)⁴⁵ and additionally quantified objectively with the psychomotor-vigilance task (PVT)⁴⁶. Except PSQI, all of the above-mentioned sleep and vigilance screening assessments are performed on both experimental sessions (session 3 and 4). All sleep and vigilance screening will be performed by the PI or a member of the research team.

Additional Questionnaires will be used to collect information about the participant's demographics including age, gender, level of education in addition to medication intake (Appendix 2).

To reduce the burden for those participants who have participated in a study at the Stroke Recovery Research Center involving the same standardized assessments and questionnaires and consented to data sharing, we will use the already available data if these have been collected within ≤30 days.

Two-layered Learning Task (sessions 3 and 4). We will adapt an established sequence learning paradigm^{47,48} for the use in patients with sensorimotor impairment of the upper extremity. Two layers of implicit sequential information (Figure 1) are implemented in the experimental paradigm through visual stimuli on a computer screen to distinguish the two modes of implicit learning. Behavior is captured with whole-hand grip-force transducers (the hand-held interface) requiring minimal active range of motion and voluntary muscle force.

[figure not shown]

Figure 1 Behavioral paradigm and participant flow. A) Experimental set-up showing visual stimuli with imperative cue (green) and force feedback (yellow) to implement the stimulus-response mapping of cue positions and input force level scaled relative to individual

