Imaging Parameters (sessions 3 and 4). Scanning will take place at the Center for Biomedical Imaging on the Siemens 3T Prisma. Functional and structural scanning parameters are detailed in the **NI Core**. High-resolution structural, fluid-attenuated inversion recovery (FLAIR), diffusion-weighted (DWI), and arterial spin labeling (ASL) perfusion imaging will use in-house standard sequences and will be collected from all participants in session 3. The task-based fMRI sequence will be optimized for an event-related design with a TR of 2 seconds. For the resting-state data, a TR of 0.8 seconds will be used. Task-based and resting-state imaging will be collected in session 4 with varying protocols for participants of SG and CG as described in the timeline below and explicitly detailed in the information and consent form. All MRI sequences will be accompanied by electrical recording of physiological signals from the upper body (e.g., electrocardiogram, electrodermal analyses) to support processing of MRI data and for secondary analyses examining relationships between autonomic nervous system dysfunction, brain, and behavioral outcomes.

D2. TIMELINE

Participants of both groups (stroke, control) will undergo the same protocol, which includes 4 sessions (outlined in the table below).

Session Number	Task Description	Location at Medical University of South Carolina	Approximate Time Commitment
0	Telephone Eligibility Screening 
 • Sensorimotor function screening (Appendix 1) • Cognitive screening (TICS^{26,27}) • MRI Safety Screen 	Via telephone	30 minutes
1	Consent	Stroke Recovery Research Center or remotely through electronic consent	20-30 minutes
2	Multi-system Assessment 
All participants
 
 • Pregnancy Test • EHI[§] • Questionnaires (Appendix 2)[§] • Neuro-Cognitive and emotion Assessment 
Stroke group
 
 • physical Assessment of upper-extremity sensorimotor functioning • NIH-SS 	Stroke Recovery Research Center or partly remotely [§]	3 – 3.5 hours

	
 • SIS[§] 		

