3	
MRI scanning and task familiarization
 
 • MRI Safety Screen • Sleep and vigilance screening 
MRI sequences:
 
 • FLAIR • DWI • ASL • T2* weighted sequence (resting-state) • Physiological recordings 
Learning task:
 
 • Task familiarization (in the mock scanner) 	Center for Biomedical Imaging	2 – 2.5 hours
4	
MRI scanning during task practice
 
MRI Safety Screen
 
Sleep and vigilance screening
 
MRI sequences:
 
 • High-resolution T1 weighted • T2* weighted sequence (task-based) during task practice • Physiological recordings 	Center for Biomedical Imaging	2 – 2.5 hours

D3. DATA ANALYSIS

D3.1 Sample Size Justification.

Given the scarcity of pilot data on stroke and control participants and fMRI-based dynamic connectivity during motor learning, justification has to be based on our best estimates and regarded with some caution. One of the primary goals of this project is to determine effect sizes for the follow-up grant proposal. For changes to latent connectivity characteristics induced by implicit motor learning (pre/post evaluation), empirically obtained effect size estimates were derived from the average effect size of published studies involving participants with chronic stroke⁹ and healthy volunteers⁵⁰. Consequently, sample sizes of 25 and 15 in the stroke survivors and healthy volunteers will allow us to estimate the for the main effect of time (pre/post learning) the within-group effect sizes can be expected to be in the range of 0.33 - 0.52 at 90% confidence level.

D3.2 Analysis Plan.

Imaging Preprocessing. Data will be processed by the CBI Computational Core led by [name]. Preprocessing parameters for the task-based fMRI data will be optimized to fit the requirements of the representational similarity analysis (RSA, described below), specifically smoothing will be reduced to allow for better multivariate pattern detection. Resting-state fMRI data will undergo in-house standard preprocessing.

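### The imaging schedule in D1.4 and D2 does not agree on the resting-state session or on group differences, and D3.2 defines no time contrast for the pre/post learning effect on which D3.1 rests

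*Combined protocol and SAP*

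**What the plan says.** **Schedule.** Under Imaging Parameters, D1.4 states: "Task-based and resting-state imaging will be collected in session 4 with varying protocols for participants of SG and CG". It adds that the variation is "as described in the timeline below" and is also set out in the consent form. The D2 timeline opens with "Participants of both groups (stroke, control) will undergo the same protocol". Its session 3 row contains the entry "T2* weighted sequence (resting-state"). Its session 4 row lists a high-resolution T1 and task-based imaging, with no resting-state entry. Stroke-only items appear in session 2 and in neither imaging row. For high-resolution structural imaging, D1.4 says that it "will be collected from all participants in session 3".

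**Effect and analysis.** D3.1 names the estimation of effect sizes for the follow-up grant as a primary goal. It rests on a within-group main effect of time, before versus after learning, with 25 stroke and 15 control participants, and gives a range of 0.33 to 0.52 at 90% confidence. In D3.2 the task model has regressors of interest for cue types. Betas are extracted per stimulus and run within each participant, and pattern-correlation matrices are formed per region. These are averaged over the participants of each group, and only then correlated between regions (second-order RSA). The resting-state analysis describes fluctuation over sub-blocks of a scan and is meant to supply biomarkers of recovery and candidate predictors of learning. D3.4 adds a univariate connectivity analysis without giving its model.

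**The concern.** The passage that describes the imaging and the timeline it points to do not agree. If acquisition does differ by group, that difference is confounded with the stroke-versus-control comparison of Aim 1.

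The second part bears on what the pilot is for. It is meant to supply effect sizes for a later application, and the effect named is a change over learning. If the analysis section never says which data before are compared with which data after, and removes the participant level before the between-region similarity is computed, that quantity cannot be obtained by following the plan.

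**Working it through.** **1. Schedule, side by side**

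| Item | D1.4 | D2 |
|---|---|---|
| Resting-state imaging | session 4 | session 3 row only |
| Task-based imaging | session 4 | session 4 |
| Group difference in imaging | yes, said to be shown in the timeline | none shown; same protocol stated |
| High-resolution structural imaging | session 3 | T1 in the session 4 row |

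Only the task-based entry agrees. D1.4 does not say that rest is scanned in session 4 alone, so rest in both sessions would satisfy D1.4 and the session 3 entry of D2. The session 4 row of D2 would then lack an entry.

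D1.4 titles the task section "Two-layered Learning Task (sessions 3 and 4"), and the session 3 row of D2 contains "Task familiarization (in the mock scanner"). A session 4 rest scan would therefore follow some task exposure under either text, in all 25 + 15 = 40 main-study participants. Under D2 the rest scan may precede it, since the order within session 3 is not given. Whether familiarization exposes the learned sequences is not stated.

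**2. Where a time contrast could sit**

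- Task model (D3.2): cue-type regressors and no term for phase or time. Betas are available per run, but no comparison of runs is defined.
- Resting-state analysis (D3.2): variation within a scan. Neither D1.4 nor D2 lists separate rest scans before and after learning.
- Univariate connectivity (D3.4): named, with no time term.
- Sleep and vigilance screening (D1.4): refers to training and retest sessions, whereas D2 has familiarization in session 3 and practice in session 4.
- Aim 1: says that change will be followed throughout acquisition, which states an intention but defines no contrast.

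The data type is also open. Aim 1 points to task data, while the title of the healthy-volunteer study cited in D3.1 concerns resting-state networks.

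**3. What the second-order RSA yields**

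Let M(i, r) be the first-order matrix of participant i in region r. As written, the plan forms

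M̄(g, r) = mean of M(i, r) over participants i in group g,

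S(g, r, r′) = Pearson correlation of the upper triangles of M̄(g, r) and M̄(g, r′).

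S has no participant index and no time index. Each pair of regions gives one number per group, with no between-participant variance. A standardized within-group change needs the mean and SD of a participant-level change:

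D(i, r, r′) = S(i, r, r′, late) − S(i, r, r′, early).

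That would give 25 and 15 values per pair of regions, with 25 − 1 = 24 and 15 − 1 = 14 degrees of freedom.

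**4. The stated range of 0.33 to 0.52**

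Read as the half-width of a 90% interval for a standardized change, z(0.95)/√n gives:

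- n = 25: 1.645/5 = 0.329, which matches 0.33.
- n = 15: 1.645/3.873 = 0.425, which does not match 0.52.

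With t quantiles the values are 0.342 and 0.455. At the 95% level with z they are 0.392 and 0.506. With the SD of change implied by a pre/post correlation of 0.25 they are 0.403 and 0.520. None of the variants tried returns both ends. The source effect sizes are not in the documents, so the range can be neither reproduced nor called wrong.

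Read instead as an expected standardized mean change d (an assumption), the 90% interval comes from inverting the noncentral t with n − 1 degrees of freedom and noncentrality d√n:

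| n | d | 90% interval | Half-width |
|---|---|---|---|
| 25 | 0.33 | −0.011 to 0.665 | 0.338 |
| 25 | 0.52 | 0.164 to 0.866 | 0.351 |
| 15 | 0.33 | −0.112 to 0.761 | 0.437 |
| 15 | 0.52 | 0.058 to 0.965 | 0.454 |

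The approximation 1.645 × √(1/n + d²/(2n)) agrees closely: 0.338 and 0.351 for n = 25, 0.436 and 0.452 for n = 15.

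**The case against.** The strongest reply is that this is incomplete wording in a pilot.

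- **Rest in both sessions** fits D1.4 and the session 3 entry of D2. This stands. A reader might infer that no single schedule can satisfy both sections; the documents do not support that for the rest scan. What remains is an incomplete table.
- **Same protocol** in D2 introduces a table that has stroke-only items in session 2, so it may mean the same session structure. The consent form and Figure 1, which are not in the public copy, may describe the variation. This stands in part. D1.4 names the timeline as well as the consent form, and the timeline shows no difference in imaging. A reader might infer that the Aim 1 comparison is confounded; the documents do not say what varies, so this is only conditional.
- **Participant-level data exist.** Per-run betas and first-order matrices are formed within participant, and D3.1 does not assign the pre/post effect to the RSA. This stands. A reader might infer that the study cannot estimate its effect size at all; that goes too far. The gap lies in the second-order step and in the missing contrast. Resampling over participants could give an interval for a group-level value, but none is described, and it would still need a time contrast.
- **Caution is declared.** D3.1 and D3.4 concede uncertain estimates and limited power. Those remarks concern precision and do not supply the contrast.
- **The half-widths** follow from 25 and 15 participants under an assumed metric. This stands: they do not measure the defect or show that the sample is too small for a pilot aimed at estimation.

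**Conclusion.** Both parts hold and should be fixed.

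(a) D1.4 and D2 disagree on the resting-state session, on the session for high-resolution structural imaging and on whether imaging differs by group. The documents do not show which text is intended. The size of any consequence cannot be computed from them.

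(b) The within-group pre/post effect on which D3.1 rests has no contrast in D3.2. The second-order RSA as written leaves one value per pair of regions per group, against the 25 and 15 participant values needed for an effect size with an interval. This follows from the order of operations and needs no assumption about the data, except that no step is carried out beyond those described.

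The half-widths of about 0.34 to 0.35 (n = 25) and 0.44 to 0.45 (n = 15) are context only, and hold if the stated range is a standardized mean change. A reader might also infer that a rest scan after task exposure is an error. The documents do not establish that, because they do not say what familiarization exposes. It is a matter for the sponsor to weigh when reconciling the schedule.

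**What to change.** 1. Reconcile D1.4, D2 and the consent form into one imaging table giving session, sequence, order and group. If acquisition differs by group, base the stroke-versus-control comparison on the data acquired in common. When settling the order, consider whether the rest scan used as a predictor of learning should precede task exposure.
2. State in D3.1 and D3.2 which data carry the pre/post effect: session 4 task runs, a session 3 versus session 4 comparison, or named rest scans. Align the training and retest wording in D1.4 with D2.
3. For task data, compute second-order similarity per participant and take the early-versus-late (or pre/post) difference per participant before any averaging. Since D1.4 says "as left and right hand will be tested", do this within hand where run order allows, and say so where it does not. Report the mean standardized change with its 90% interval in each group, and the group difference in change. Group-averaged matrices can stay for description. If rest scans carry the effect, define the participant-level change in the same way.
4. State the metric of 0.33 to 0.52 and whether it is an expected effect or a precision figure, and give the expected half-widths for n = 25 and n = 15.

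**Cost.** Wording in D1.4, D2, D3.1 and D3.2, a check of the consent form with an amendment if it differs, and a little more analysis. Participant-level similarity values are noisier than group-averaged ones. The number and order of runs and their allocation to hands are not stated, so it cannot be confirmed that a within-hand contrast needs no change to the task. The schedule is best settled before scanning, since acquisition order cannot be changed afterwards.
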